13.2.2 Expectedness Assessment

The SC Project Lead will be responsible for determining whether an AE is expected or unexpected. Only severe (Grade 3 or higher) AEs that are directly related to DBS collection/venipuncture are considered reportable for this study; as such, these will be the only events that will be graded for expectedness. An AE will be considered unexpected if the nature, severity, and/or frequency of the event is not consistent with the risk information previously described for DBS collection/venipuncture.

For example, using this definition, an infection that is judged to be a direct consequence of the DBS collection/venipuncture, requires antibiotic treatment, and causes a missed day of work may be considered "expected"; an infection that causes an extended absence from work or that leads to hospitalization for further treatment may be considered "unexpected." As previously noted, the SC Project Lead will determine expectedness; the Emmes Medical Monitor will be available to provide advice regarding such decisions, if necessary.

13.2.3 Relationship Assessment

The SC Project Lead will assess the relationship of each AE to the DBS collection/venipuncture. The SC Project Lead will use clinical judgment in conjunction with the assessment of a plausible biologic mechanism, a temporal relationship between the onset of the event in relation to the DBS collection/venipuncture, and identification of possible alternate etiologies including underlying disease, concurrent illness, or concomitant medications. Relatedness of an AE is often assessed by asking 'Is there a reasonable possibility that the DBS collection/venipuncture caused the event?' The relatedness between the AE and the DBS collection/venipuncture will be presumed unless a clearly recognized alternate etiology is identified. Alternative explanations for clinical or laboratory abnormalities must be sought before discontinuing study participation.

The following guidelines should be used to assess the relationship of an AE to the DBS collection/venipuncture and only a physician can make this determination.

Relationship	Description
Related	The AE is known to occur with DBS collection/venipuncture, there is a reasonable possibility that the DBS collection/venipuncture caused the AE, or there is a temporal relationship between the DBS collection/venipuncture and event. Reasonable possibility means that there is evidence to suggest a causal relationship between the DBS collection/venipuncture and the AE.
Not related	There is not a reasonable possibility that the DBS collection/venipuncture caused the event, there is no temporal relationship between the DBS collection/venipuncture and event onset, or an alternate etiology has been established.

13.3 Safety Reporting Requirements

13.3.1 Adverse Event Reporting

The AE reporting period begins at the signing of informed consent and continues through the end of study participation.

A reportable AE for this study is defined as an event that is considered both related to the DBS collection/venipuncture and is severe (Grade 3 or higher).

If an AE also meets the definition of an UP (see Section 12.2.1), the AE must be entered in the EDC system within 3 business days of the SC staff becoming aware of the event.

NOTE: The SDMC Safety team will not have any responsibility to evaluate or to follow any reported social harms or unanticipated problems that do not qualify as AEs/SAEs.

If an AE meets the definition of an SAE (see Section 13.1.2), the SAE reporting procedure must be followed (see Section 13.3.2).

All other AEs must be entered in the EDC system within 7 calendar days of the SC staff becoming aware of the event. These AEs will be reviewed by the Protocol Team during their regular study monitoring meetings and by the DSMB as part of their routine DSMB reports/meeting. AEs will also be reported to Sterling IRB/local IRBs in the annual report.

The SC Project Lead is responsible for acquiring as much information as possible to determine the causality and outcome of a reportable AE and to determine whether a medical event meets criteria for an SAE. Follow-up of the AE is required until the event has resolved, returned to baseline, or has been deemed stable and is not expected to worsen, based on the judgment of the SC Project Lead. All events must be followed until resolution. Events that are unresolved at 30 days after the safety monitoring period ends will be documented using the last known status of the event.

13.3.2 Serious Adverse Event Reporting

Any event that meets the criteria defined in Section 13.1.2 is reportable as an SAE regardless of the determination of relatedness to the DBS collection/venipuncture.

The SAE reporting period begins at the signing of informed consent and continues through the end of study participation.

Grade 4 (life-threatening) or Grade 5 (fatal) SAEs must be entered in the EDC system within 3 reporting days of SC awareness (see ATN MOGO Chapter 8 Appendix B for the definition of "reporting day").

The primary means of reporting will be through completion of the SAE eCRF in the EDC system. If the eCRF is not available or data cannot be transmitted (e.g., internet not functional), a scanned copy of the paper SAE form can be submitted to the SDMC Safety Team via email ([contact]). The SAE eCRF must then be completed in the EDC system as soon as the system becomes available.

If an SAE is unexpected and has a reasonable possibility of being related to the study, the SC Project Lead will submit the SAE to Sterling IRB within 1 business day of SC awareness if the event is life-threatening or fatal, otherwise submit within 10 business days of SC awareness. Furthermore, the SC Project Lead will report SAEs to their local IRB per institutional guidelines.

Upon entry of an SAE eCRF in the EDC system, a notification will be automatically generated and sent to the Protocol Co-Chairs, Study Manager, NICHD Representatives, OCC Regulatory Affairs Unit, and the SDMC Safety Team, inclusive of the SDMC Medical Monitor. Within 24 hours of the event's entry in the EDC, the SDMC Medical Monitor will perform a preliminary assessment of the relationship of the SAE to the DBS collection/venipuncture and the expectedness of the event to determine the reporting status to the regulatory authorities and to other stakeholders. The SDMC Medical Monitor will prepare the SAE report and send it to the

NICHD Representatives for review and comment. The Protocol Co-Chairs and Study Manager will be copied on the communications between the medical monitor and representatives. The final assessment of the relationship of the SAE to the DBS collection/venipuncture and the expectedness of the event determines the reporting status to Sterling IRB and other regulatory agencies, as applicable. The DSMB Chair will be informed of all SAE reports in real time via email.

Additional information may need to be gathered to evaluate SAEs and to complete the appropriate eCRFs and the summary. This process may include obtaining hospital discharge reports, medical records, autopsy records and/or any other type records or information necessary to provide a complete and clear picture of the SAE and events preceding and following the event. If the SAE is not resolved or stable at the time of the initial report or if new information becomes available after the initial report, follow-up information must be submitted as soon as possible.

Like AEs, each SAE must be followed until the event has resolved, returned to baseline, or has been deemed stable and is not expected to worsen, based on the judgment of the SC Project Lead. If the event resolves during the study or follow-up period, a resolution date should be documented.

14. Statistical Considerations

This section summarizes the primary features of the statistical analysis for the study. A statistical analysis plan (SAP) will be prepared and finalized prior to database lock and will specify all analyses to be performed. Major changes in the analysis (e.g., redefinition of analysis methodology of a primary endpoint) should result in a protocol amendment. Minor changes, deviations, or changes from the statistical analyses specified in the protocol will be described and justified in the SAP and/or the final study report.

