13.1.2 Serious Adverse Events

An AE is a "serious adverse event (SAE)" if, in the view of the SC Project Lead, Protocol Team, or NICHD, it results in any of the following outcomes:

- Death;
- A life-threatening AE (An event is considered "life-threatening" if, in the view of the SC Project Lead or Protocol Co-Chairs, its occurrence places the participant at immediate risk of death, inclusive of suicide attempts);
- Inpatient hospitalization (admission) or prolongation of existing hospitalization;
- A persistent or significant incapacity or substantial disruption of the ability to conduct normal life functions;

- A congenital anomaly/birth defect; or
- Important medical events that may not immediately be life-threatening, or result in death or require hospitalization, but require intervention to prevent one of the other outcomes listed above. Examples of such medical events include allergic bronchospasm requiring intensive treatment in an emergency room or at home, blood dyscrasias or convulsions that do not result in inpatient hospitalization, or the development of drug dependency or drug abuse.

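### Sections 13.2.2, 13.2.3 and 13.3.2 set conflicting standards for SAE relatedness and expectedness, and the causality assessment they define cannot attribute an SAE to the behavioural intervention

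*Protocol*

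**What the plan says.** Section 13.3.2 makes every event that meets the SAE definition reportable, whatever its relation to blood collection. Its condition for site submission to the IRB begins "If an SAE is unexpected and has a reasonable possibility of being related to the study". Submission is due within 1 business day if the event is life-threatening or fatal, and within 10 business days otherwise. Later in the same section, after a preliminary review by the medical monitor, the "final assessment of the relationship of the SAE to the DBS collection/venipuncture and the expectedness of the event determines the reporting status" to the IRB and other agencies.

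The terms used there are defined in Section 13.2:

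- **Relatedness (Section 13.2.3):** "The SC Project Lead will assess the relationship of each AE to the DBS collection/venipuncture". The Not related category begins "There is not a reasonable possibility that the DBS collection/venipuncture caused the event". Neither category refers to the counselling sessions or to any other study procedure.
- **Expectedness (Section 13.2.2):** for Grade 3 or higher AEs directly caused by blood collection, "these will be the only events that will be graded for expectedness". The reference is the known risk of blood collection.

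Section 13.1.2 counts as life-threatening an event that "places the participant at immediate risk of death, inclusive of suicide attempts".

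**The concern.** Blood is taken on the same schedule in both arms (Section 3, Appendix 1). What differs is the behavioural intervention: ten sessions in IMPACT against two in eSOC, so 10 − 2 = 8 additional sessions (Sections 6.1.1 and 6.1.2). The one defined causality question therefore concerns an exposure that the arms share and leaves out the one under test.

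The protocol itself treats the omitted route as plausible. Section 1.2 describes depression and suicidality alongside stimulant use, and low mood and isolation after use stops. Section 12.1.2 lists suicidal ideation and depression among events that might be connected with study activity.

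Two things are at stake. Site and medical monitor can apply different tests to the same SAE and disagree on whether it goes to the IRB. And a later statement that no related SAEs occurred would mean only that none was attributed to a blood sample.

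**Working it through.** No arithmetic applies. The check sets the rules side by side and follows one event through them.

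| Rule | Relatedness judged against | Expectedness covers |
|---|---|---|
| 13.2.2 | blood collection | Grade 3+ AEs directly caused by blood collection only |
| 13.2.3 | blood collection | not addressed |
| 13.3.2, site submission to IRB | the study | any SAE |
| 13.3.2, preliminary and final assessment | blood collection | any SAE |
| 12.2.1, unanticipated problems | participation in the research | research procedures and population |

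Take a suicide attempt in an IMPACT participant that the site thinks may be linked to the sessions.

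1. It is an SAE under Section 13.1.2 and is reportable under Section 13.3.2.
2. Relatedness under Section 13.2.3: blood collection is not a reasonable cause and another cause has been identified, so the category is Not related. The form of assessment described has nowhere to record the suspected link to the sessions.
3. Expectedness: Section 13.3.2 needs it, Section 13.2.2 excludes this event from grading, and the only reference supplied is blood-collection risk.
4. IRB status by the site test: if the event is judged unexpected and possibly related to the study, it must be submitted within 1 business day.
5. IRB status by the final assessment: relation to blood collection is absent, so this sentence gives no basis for submission.

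Steps 4 and 5 come from the same section and point in opposite directions.

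Now suppose the same attempt follows shortly after a blood sample and no other cause is established. Section 13.2.3 says that relatedness "will be presumed unless a clearly recognized alternate etiology is identified", and a temporal relationship alone is enough for the Related category. The event could then be labelled related, but to the blood sample. The attribution is misdirected instead of missing.

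There is one further inconsistency. The note opening Section 12 relieves the data centre's safety team of evaluating any social harm or unanticipated problem. The note in Section 13.3.1 is narrower: the team "will not have any responsibility to evaluate or to follow any reported social harms or unanticipated problems that do not qualify as AEs/SAEs". An SAE that is also an unanticipated problem is excluded by the first note and not by the second.

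**The case against.** The strongest defence is that little is lost in practice, and much of it stands.

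- **Capture.** Every SAE is entered whatever its cause and notified to the safety team, medical monitor and sponsor representatives, and the DSMB Chair is told in real time (Section 13.3.2).
- **Comparison by arm.** Section 14.3.6 summarises SAEs by group, and Section 11.6 has the DSMB review safety data by arm about three times a year. An excess of suicide attempts on IMPACT would be visible without any causality label.
- **Other IRB routes.** The site test in Section 13.3.2, the unanticipated-problem route (Section 12.2) and the social-harm route (Section 12.1.2) all rest on relation to the study or research, with the same limits of 1 and 10 business days.
- **Context.** Limiting non-serious AE reporting to severe blood-collection events is a stated choice for a low-risk study without an investigational product (Section 13), and psychosocial harm is routed through Section 12.

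A reader might infer that intervention-related SAEs would escape the IRB, that the DSMB could not see them, or that every SAE not caused by blood sampling is Not related by definition. The documents do not support these readings. The first two are answered by the routes above. The third is contradicted by the presumption of relatedness and the temporal criterion in Section 13.2.3. Nor does the safety-team note close off the unanticipated-problem route for SAEs, given the qualifier in Section 13.3.1.

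The defence does not remove the contradiction. The alternative routes need someone to judge relation to the research separately, while the SAE assessment asks only about blood collection and is said to settle IRB status. An arm-level count also does not replace a case-level judgement when SAEs are few.

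**Conclusion.** The point holds as a contradiction in the reporting rules. Section 13.3.2 states two IRB criteria that can conflict for the same SAE. Section 13.2.2 excludes from expectedness grading most of the events for which Section 13.3.2 requires it. Section 13.2.3 offers no way to attribute an SAE to the exposure that differs between arms. The consequence is contradictory criteria and missing or misdirected causality; loss of events or certain failure to report is not shown.

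No figure can be attached, because the documents give no expected SAE count. The conclusion rests on reading the three sections as written. The SAE form and its completion guide are not at hand and might already contain a wider relatedness field, in which case the protocol text would still need to be brought into line with it. These definitions are fixed in the protocol, and an analysis plan cannot summarise an attribution that was not collected. The table layout itself can be left to that plan.

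**What to change.** Reconcile Sections 13.2.2, 13.2.3 and 13.3.2 as follows:

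1. For each SAE, record relatedness twice: to blood collection, and to the study intervention or any other study procedure.
2. Assess expectedness for every SAE against the research procedures and the study population, the reference that Section 12.2.1 already uses for unanticipated problems.
3. Let IRB reporting status rest on relation to the study, as the site-submission sentence of Section 13.3.2 already does, and amend the final-assessment sentence to match.
4. Align the safety-team note at the start of Section 12 with the qualified note in Section 13.3.1.

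The cost is a wording amendment, one additional field on the SAE form, and slightly more site and medical-monitor review per SAE. The restriction on reporting non-serious AEs need not change.

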14.1 Statistical Hypotheses

The hypothesis for the primary objective of determining the effectiveness of IMPACT is:

Primary hypothesis: When compared to eSOC, IMPACT will result in a reduction of distinct acts of CAS from baseline to Month 12 post-intervention initiation.

- **Null hypothesis:** The rate of distinct acts of CAS will be the same between individuals assigned to the IMPACT intervention and those assigned to the eSOC arm.
- Alternative hypothesis: The rate of distinct acts of CAS among individuals assigned to the IMPACT intervention will be different from the rate among individuals assigned to the eSOC arm.

The hypothesis for the key secondary objective of determining the effectiveness of IMPACT on stimulant use is:

Key secondary hypothesis: When compared to eSOC, IMPACT will result in a reduction of stimulant use from baseline to Month 12 post-intervention initiation.

- **Null hypothesis:** The rate of stimulant use will be the same between individuals assigned to the IMPACT intervention and those assigned to the eSOC arm.
- Alternative hypothesis: The rate of stimulant use among individuals assigned to the IMPACT intervention will be different from the rate among individuals assigned to the eSOC arm.

14.2 Sample Size Considerations

Careful consideration was given to the effect size used in the power analysis and is estimated based on data from previous studies. In our pilot study, the mean difference in CAS acts between the intervention versus control arm at 6 months was 4.7 (>50% reduction). Although the pilot study had a large effect on reductions in sexual risk behaviors, effect sizes from small studies like the pilot study are less reliable and frequently inflated.^[70] Additionally, in the present study, the eSOC comparison group will be receiving two RR sessions and, as such, they will likely also decrease their engagement in CAS. Therefore, the study is powered to detect a 20 percent (or greater) reduction in the number of CAS acts between groups in the 12-month follow-up period, expecting both groups to show improvements from baseline. This decision will account for the fact that in clinical trials in general, and HIV behavioral trials in particular, when the control group receives any of the intervention content, it is more difficult to find a between-group difference^[71-73] as well as take into account the fact that the primary timeframe in the present study is 12 months instead of 6. Lastly, a 20 percent or greater reduction in the number of CAS acts has been previously described as a clinically meaningful change related to HIV sexual risk outcomes.

Moreover, to ensure sufficient power to assess whether intervention effectiveness differs between intervention delivery format (i.e., virtual vs. in-person) with a power of 90 percent, alpha level of 0.05, 291 participants will need to complete the proposed intervention in order to examine difference between IMPACT (n=194) and eSOC control (n=97). We plan to randomize 360 participants (n=240 in IMPACT and n=120 in eSOC) to account for 20 percent attrition at the month 12 visit.

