Participants will be followed for 1 year, with assessments at enrollment and Months 4, 8, and 12. Figure 1 (Flow Diagram of Study) provides a schematic of the study. At each time point, participants will provide a urine sample and a blood sample, and complete a self-report psychosocial and sexual risk assessment battery. Primary outcomes include the number of CAS acts while not protected by PrEP (YGBSMM NLWHIV) or while not virally suppressed (YGBSMM LWHIV) and stimulant use. We will also test our multifaceted implementation strategy by assessing adoption/accessibility and implementation using mixed-methods assessments that describe and examine characteristics of successful implementation (including differences by intervention delivery format). Finally, we will assess the feasibility of maintenance and sustainment of Project IMPACT by using the well-established CEPAC-AYA model to project its cost-effectiveness on HIV transmissions, quality-adjusted life years, and perperson lifetime costs.

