4.1 Inclusion Criteria

To be considered eligible for enrollment, an individual must meet all the criteria listed below:

- 1. Age 16-24 years, inclusive, at enrollment;
- 2. Assigned male at birth;
- 3. Identifies as a cisgender boy or man;
- 4. Self-reports CAS with another boy/man—receptive or insertive—while using stimulants (1 hour prior to, or during, sex) within the last 4 months; *stimulants* is defined as crystal methamphetamine, cocaine, and MDMA (e.g., ecstasy, molly); and
- 5. Willing and able to provide written informed consent for study participation.

In addition, virtual participants must meet all the criteria listed below:

- 1. Access to a computer/smartphone/tablet that can use video chat (e.g., Zoom or Google Meet);
- 2. Provide a mailing address where they can receive a package;
- **3.** Access to stable internet that they can use for more than 2 hours at a time;
- 4. Have a private place (where no one else can see or hear) where they can complete visits online; and
- **5.** Reside within the continental U.S.

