14.3 Statistical Analysis Methods

14.3.1 General Analysis Considerations

All data collected will be summarized and/or listed. Analyses will be performed using SAS[®] software (SAS Institute Inc., Cary, NC) version 9.4 or higher.

Unless otherwise specified, descriptive statistics include the mean, SD, median, minimum, maximum for continuous variables, and the number and proportion in each group for categorical variables. Unless otherwise specified here or in the SAP, statistical tests and confidence intervals (Cis) will be computed using a two-sided 5 percent significance level. Exact Cis will be used for univariate summaries of dichotomous variables, and Wald- or score-based Cis will be used for mean/rate differences/ratios. All proportions will use as denominator the number of subjects contributing data at the specified time point within the specified group and analysis population. Summaries will be presented by intervention and by time point, where relevant.

For all summaries outlined in this section, the SAP will contain additional detailed descriptions of the analyses to be conducted.

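### Section 14.2 attaches 90% power to 291 completers without a control rate, a dispersion or a clear comparison; for a 20% main effect it needs a person-level CV of about 0.55 or less, and it cannot also hold for a format difference of that size

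*Protocol*

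**What the plan says.** Section 14.2 of the protocol makes two power statements.

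- The first concerns the main effect: "the study is powered to detect a 20 percent (or greater) reduction in the number of CAS acts between groups", over the 12-month follow-up. No power figure stands with it.
- The second opens a new paragraph and concerns delivery format. Its stated purpose is "to ensure sufficient power to assess whether intervention effectiveness differs between intervention delivery format", and it continues "with a power of 90 percent, alpha level of 0.05, 291 participants will need to complete the proposed intervention". The sizes it then gives are for the two arms, not for the arms within each format: "in order to examine difference between IMPACT (n=194) and eSOC control (n=97").

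Attrition follows: "We plan to randomize 360 participants (n=240 in IMPACT and n=120 in eSOC) to account for 20 percent attrition". Section 3 calls the study well powered for differences by format, and section 5.6 gives the format comparison as the reason for the 2:1 ratio.

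Section 14.2 reports one pilot mean difference in acts. It gives no control rate, standard deviation, CV, overdispersion or within-person correlation.

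On the endpoint, section 3 counts "the number of CAS acts while not protected by PrEP (YGBSMM NLWHIV) or while not virally suppressed (YGBSMM LWHIV"). Sections 2.2.1 and 14.3.3 instead define an act as one lacking a condom or lacking the protection of PrEP or viral suppression. Section 4.1 admits on "Self-reports CAS with another boy/man" while using stimulants, and excludes nobody for being protected. The primary model in section 14.3.3 is a marginal Poisson model with an arm effect and no baseline covariate.

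**The concern.** The power of a count comparison depends on how much counts vary between people, and section 14.2 fixes a power and a sample size without stating that variation. Counts of sexual acts can vary widely between people, and this endpoint may add zeros of its own: under the section 3 wording, a participant who stays on effective PrEP or stays virally suppressed contributes nothing, whatever his behaviour. The planned model has no baseline covariate to absorb between-person variation.

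The 90% is also attached to a question about format while the sizes are those of the arm comparison. An interaction needs much more information than a main effect, so one figure cannot serve both at the same effect size. A reader of the final report would not know what the trial was able to detect on either question.

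**Working it through.** **Inputs.** Rate ratio 0.80, power 0.90, alpha 0.05 and arms of 194 and 97 (section 14.2). Two-sided, from section 14.3.1: "statistical tests and confidence intervals (Cis) will be computed using a two-sided 5 percent significance level". The summary is a rate ratio (section 14.3.3). The CV is not in the protocol and is treated as unknown; it is that of a person's count over the whole follow-up, so having three visits does not relax it.

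**Attrition step.** 291/0.80 = 364, and 360 × 0.80 = 288. This agrees with the stated 360 to within rounding.

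**The 291.** It cannot be reproduced forwards, because no rate or variance is stated. It can only be solved backwards.

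**Main-effect reading.** For a Wald test on the log rate ratio:
- SE needed = ln(1.25)/(1.960 + 1.2816) = 0.2231/3.2415 = 0.0688.
- SE = CV × sqrt(1/194 + 1/97) = CV × 0.1244.
- CV = 0.0688/0.1244 = 0.55.

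Variants for a two-sided 90% main effect: 0.50 (difference scale, common SD), 0.53 (SD proportional to the mean) and 0.62 (log scale, all 360 with full data). A pure Poisson count would give 291 at a control mean of (1/(194 × 0.8) + 1/97)/0.0688² ≈ 3.5 acts over follow-up.

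**Power and detectable effect at 194 and 97, with CV assumed:**

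| CV | Power for RR 0.80 | RR detectable at 90% |
|---|---|---|
| 0.55 | 90% | 0.80 |
| 0.75 | 67% | 0.74 |
| 1.0 | 43% | 0.67 |
| 1.5 | 22% | 0.55 |

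For example, at CV 1.0, 0.2231/0.1244 = 1.794; 1.794 − 1.960 = −0.166, giving 43%. The detectable RR is exp(−3.2415 × 0.1244) = 0.67.

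**Format reading.** With two equal formats, each log rate ratio has twice the overall variance, so their difference has four times the variance and twice the SE. For a ratio of rate ratios of 0.80:
- the CV ceiling halves, to 0.55/2 ≈ 0.28;
- if the main effect has 90% power, the interaction z is 3.2415/2 = 1.621; 1.621 − 1.960 = −0.339, giving about 37%.

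**Share of zeros.** If a share p always scores zero and everyone else has identical counts, CV² = p/(1 − p). Setting CV = 0.554 gives p = 0.306/1.306 = 23.5%. Simulated Poisson counts with mean 30 to 100 among the unprotected give 83–86% power at that share and 55–58% at 40%. If the unprotected themselves have CV 0.55, then CV² = (1 + 0.55²)/(1 − p) − 1, and p of 20%, 30% and 40% gives power of 62%, 49% and 38%. Every share here is an assumption.

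**The case against.** The strongest reply is that the protocol never states 90% power for a 20% reduction with 291 people. That joins two sentences, and the one with the numbers is about format. This stands: the pairing is an inference from the 194/97 split. It does not help the plan, since the literal reading has the lower ceiling.

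Second, the ceiling is not a sharp 0.55. Section 14.3.2 analyses everyone randomized, and weighted GEE uses the earlier visits of those who drop out. This also stands, and the range of 0.50 to 0.62 allows for it. Even with full data on all 360, power at CV 1.0 is about 51%.

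Third, the zeros depend on the section 3 wording. Read literally, sections 2.2.1 and 14.3.3 would not zero every protected act. Nor does any document give a protected share; section 1.2 describes poor PrEP adherence and more detectable viral loads among stimulant users, which does not suggest a high one. So the 23.5% is a threshold, not an estimate.

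Fourth, the pilot may seem reassuring. If the brackets in 2.24 [0.2] and 6.94 [0.4] (section 1.2.2.3) were standard errors of person means, the CVs would be 0.2 × sqrt(21)/2.24 = 0.41 and 0.4 × sqrt(20)/6.94 = 0.26. But they are unlabelled model output for acts while using stimulants, and 0.2 is below even the Poisson value sqrt(2.24/21) = 0.33, so they establish no person-level CV. Conversely, a reader might infer from the pilot's days of stimulant non-use that variance was simply set equal to the mean. The CAS figures do not follow that pattern, so the inference is not supported.

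Last, reporting the rate ratio with its 95% CI (section 14.3.3) limits the misreading of a null result. That is fair, but it does not make the stated power correct.

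**Conclusion.** The point holds as a conditional statement. The 90% in section 14.2 rests on an unstated dispersion and is attached to an unclear comparison. As a main effect with a rate ratio of 0.80, it requires a person-level CV of roughly 0.50 to 0.62, and 0.55 for a log-scale test on 291. As a format difference of the same size with equal formats, it requires about 0.28. Both cannot be true at the same CV: 90% for the first means about 37% for the second. This is the firmest part of the finding, because it needs no assumed CV, only equal formats and equal effect sizes.

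A reader might go further and infer that the trial cannot detect a 20% reduction. The documents do not support that, because no figure in them shows the CV to be above the ceiling. Nor is a wrong calculation shown; the inputs behind 291 are absent. What can be said is that power falls to 67%, 43% and 22% at assumed CVs of 0.75, 1.0 and 1.5, and that a persistently protected share near 23.5% would by itself exhaust the 0.55 under the section 3 wording.

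**What to change.** Keep the sample size and revise the text.

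1. In section 14.2, say which comparison the 90% refers to, and give the control rate, the dispersion and the protected share assumed behind 291.
2. Replace the single 90% with a table of power and detectable rate ratio for IMPACT versus eSOC over a CV range such as 0.55 to 1.5.
3. Give the format interaction its own, lower power, and withdraw the claim in section 3 that the study is well powered by format.
4. Reconcile the endpoint wording in sections 2.2.1 and 14.3.3 with section 3, so that it is clear whether a protected condomless act counts.
5. Check the CV with pooled, arm-blind counts as they accrue. Follow-up counts are preferable, because eligibility requires recent CAS with stimulants and so truncates the baseline counts.

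The cost is wording, a small table and one blinded check. No participants are added. The downside is that the stated power becomes less favourable.
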